13.2.5 Written/ reading / translation considerations

Patients will not have cognitive impairment as this is a standard contraindication to undergoing renal transplantation. In the case of patients who speak no English, we will use independent advocates or standard clinical translation support services which are readily available during the consent process for the operation itself. Once consented verbally, patients will be provided with a translation of the patient information sheet and consent form.

In addition, we recognise that there are a significant number of patients who speak Bengali in our local population. We will consent these patients with a Bengalitranslated PIS and consent form.

13.2.6 Participants lacking capacity

The clinical team will not approach any patient who is felt not to have capacity to take part in the study.

13.2.7 Minors

Patients under 18 are not eligible to participate in the study.

13.2.8 Consenting process

Patients will be approached by a member of the clinical team and asked if they would like to know more about the study. If the patient is interested, the research team will contact the patient to discuss the trial. They will inform the potential participant or his/her legal representative about the nature and objectives of the trial and possible risks associated with their participation.

They will receive the PIS and have as long as they need to read it and have all their queries satisfactorily answered. However if they are unable to come to a decision 24 hours after their transplant the consent process will be abandoned and they will not take part in the trial.

The consent process will be documented in the source documents.

13.2.9 Additional consent provisions for collection and use of participant data and biological specimens in ancillary studies

Patient samples will be stored as per standard practice. These samples may only be used in future research following a substantial amendment to the protocol and ethical approval. Patients would be re-consented in such a scenario.

13.3 Screening Procedures

All participants that undergo screening will be logged into a study specific screening log.

Following informed consent being signed, and before randomisation takes place, the following information will be collected:

Inclusion/exclusion criteria Demographic data Transplant data (if appropriate) Concomitant medication Medical history

13.4 Treatment Allocation

13.4.1 Randomisation Method

The method of randomisation will be a simple randomisation using pre-filled envelopes with study numbers 1 - 50 printed on them. The envelopes will be prefilled by a doctor who is independent to the study and quality control checks will be performed and documented by an independent member of the clinical team. Inside the envelope there will be a treatment code, which will be sent to pharmacy along with the patient's study number. If a patient is randomised but does not receive any IMP/placebo they will not be included in the study and will not be replaced.

Both the patient's study number and the treatment code will be documented in the trial master file.

13.4.2 Randomisation Procedure

A spreadsheet of treatment codes (linked to either IMP or placebo) will be created using an online generator using a block randomisation sequence (Sealed Envelope Ltd. 2016. Create a blocked randomisation list. [Online] Available from: https://www.sealedenvelope.com/simple-randomiser/v1/lists [Accessed 31 Jul 2017].)

This spread sheet will be stored in the pharmacy dispensary.

Each treatment code (for example A1, A2,...A50) will be written on a card and sealed in an envelope.

At randomisation, one of these envelopes will be chosen at random to associate the patient's study ID (e.g. patient 01 or 13) to the treatment code, which will be recorded in the CRF. This linked study code and patient identification will be sent to pharmacy for dispensing. The pharmacist will use their spread sheet, which links the treatment code with the allocation of IMP or placebo.

Finally, each study participant will have their Study ID linked to their treatment allocation written on a card, which will be sealed in an envelope with their study ID on the front of the envelope (this will be created by an independent doctor). This means that breaking the study allocation will only compromise that individual patient's allocation.

The people who will have access to the envelope section are the CI and Sub-I only. The people who will have access to the treatment code (without the treatment allocation) are the study team. The people who will have access to the treatment code matched to the treatment allocation are the pharmacy team and sponsor office only. Should there be the need to break the treatment allocation, the CI or Sub

investigator will open the locked container which is stored on the renal unit to allow out of hours access, and pick out the relevant patient's ID number and open only this envelope.

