11.3.2 Secondary Endpoints

- 1) Histological staining for Treg cells in renal biopsy tissue between baseline and 3 month protocol biopsy
- 2) Incidence of delayed graft function, defined as the need for dialysis within 1 week post-transplant
- 3) Diabetic control between baseline and month 3 using change in HbA1c measurement
- 4) Dose of other anti-diabetic medication between baseline and month 3 (descriptive)
- 5) Safety endpoints: i.e. number of hypoglycaemic episodes (descriptive)
- 6) Insulin resistance: HOMA IR measurement at month 3
- 7) Graft function: (eGFR) at month 3
- 8) Episodes of acute rejection (defined as biopsy proven acute rejection)
- 9) Episodes of opportunistic infections: bacterial and viral (descriptive)

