12.1 Inclusion Criteria

- a) Females or males aged 18 years and above
- b) Having undergone renal transplantation at the Royal London Hospital within the previous 24 hours
- c) A pre-transplant diagnosis of Type 2 diabetes
- d) Provision of written, informed consent prior to any study specific procedures
- e) In women of childbearing potential* documentation of a negative pregnancy test during admission for renal transplant.

*Women of childbearing potential are defined as women following menarche until becoming post-menopausal, unless permanently sterile. Permanent sterilisation methods include hysterectomy, bilateral salpingectomy and bilateral oophorectomy. A post-menopausal state is defined as the absence of menses for 12 months without an alternative medical cause.

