13.2 Informed Consent Procedures

Informed consent will be obtained either pre-transplantation or within 24 hours posttransplantation, but prior to the participant undergoing procedures that are specific to the trial, and are outside standard routine care at the participating site (including the collection of identifiable participant data).

In the case of deceased donor transplantation, patients do not know when they will receive a transplant, and it is therefore impossible to approach patients in the days and weeks before their transplant. Patients will have already given consent to undergo their renal transplant at short notice, however some patients may be unable to give fully informed consent in the time immediately before or within 24 hours after transplant for this research study. If the PI or patient feels they are unable to give fully informed consent within the first 24 hours after the operation, then they will not be consented.

Patients who are planned to undergo live-donor transplantation will be given information about the study pre-transplantation during the assessment process, but will not be consented until they proceed with the transplant.

We hold regular pre-transplant open days to which all patients on the transplant waiting list are invited. At these open days we will inform patients of the current study opportunities. We will use the PIS as the text for these discussions and will be free to verbally discuss the study with patients on the day.

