- Hypertension (yes/no, categorical)
- Heart failure (yes/no, categorical)

Pregnancy test

• Pregnancy test negative (either serum or urine) (yes/no, categorical)

Transplant details

- Cold ischaemia time in hours (continuous)
- Warm ischaemic rime minutes (continuous)
- Donor age (continuous)
- ECD (yes/no, categorical)
- CMV mismatch (yes/no, categorical)
- HLA mismatch (categorical)

Medication

Each medication will be recorded as name/dose/start date (categorical)

Biochemical Parameters

- Fasting c-peptide (continuous)
- Fasting cholesterol (continuous)
- Haemoglobin (continuous)
- Serum sodium (continuous)
- Serum potassium (continuous)
- Serum urea (continuous)
- Serum creatinine (continuous)
- eGFR (CKD-EPI formula, continuous)
- Serum albumin (continuous)
- Serum alkaline phosphatase (continuous)
- Serum bilirubin (continuous)
- Serum alanine aminotransferase (continuous)
- Serum calcium (continuous)
- Serum phosphate (continuous)
- C-reactive protein (continuous)
- Glucose (continuous)
- Haemoglobin A1C (DCCT aligned; continuous)
- Peripheral Treg Cell number (interval)
- HOMA IR (continuous)

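### Donor type is neither in the listed transplant details nor used in the named test, so the delayed-graft-function comparison is exposed to chance donor-type imbalance

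*Combined protocol and SAP*

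**What the plan says.** **Who is enrolled.** The eligibility criterion in section 12.1 is "Having undergone renal transplantation at the Royal London Hospital within the previous 24 hours", with no restriction on donor. Section 13.2 describes consent for both routes: "In the case of deceased donor transplantation, patients do not know when they will receive a transplant", and "Patients who are planned to undergo live-donor transplantation will be given information about the study pre-transplantation during the assessment process".

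**How they are allocated.** Section 13.4.1: "The method of randomisation will be a simple randomisation using pre-filled envelopes with study numbers 1 - 50 printed on them". Section 13.4.2 instead describes a list "created using an online generator using a block randomisation sequence", with envelopes then picked at random. Neither section names a stratification factor.

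**The endpoint.** Secondary endpoint 2 in section 11.3.2 is "Incidence of delayed graft function, defined as the need for dialysis within 1 week post-transplant". Section 9.3 treats it as the measurable consequence of reduced ischaemia-reperfusion injury. Section 9.2 calls it a surrogate for early renal outcome when explaining why the dose is not titrated upwards.

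**What is recorded and tested.** The transplant details in section 19.3 are cold and warm ischaemia time, donor age, extended-criteria donor (ECD), CMV mismatch and HLA mismatch. Section 19.5 excludes subgroup analysis and names a chi-square test for categorical data. Section 19.6 adds no method for secondary endpoints. Section 19.3 defers to a SAP for full details, but the document supplied contains no separate SAP text.

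**The concern.** DGF is the clinical readout closest to the proposed early mechanism. If its risk differs between living- and deceased-donor recipients, part of any observed difference between arms may reflect donor mix. With 25 per arm, appreciable imbalance is not rare. As written, the plan neither lists the variable that would reveal the imbalance nor has an analysis that would use it.

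Section 19.1 says the pilot is meant to generate data for a larger trial. For that purpose a DGF rate or difference that cannot be read by donor type is less useful than it could be. The stake is precision and interpretation of one secondary endpoint.

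**Working it through.** The plan has no figure to reproduce: section 19.1 sets 25 per arm on feasibility, with no effect size, power or DGF rate.

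**Inputs.** From the documents: 50 patients, 25 per arm. Assumed, because the documents do not give them: L = 10, 15 or 20 living-donor recipients; DGF risk p_L = 2-8% (living) and p_D = 25-45% (deceased).

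**1. Chance of imbalance.** If all 50 envelopes are used and drawn at random, allocation acts as a random 25:25 split. The number X of living-donor recipients in one arm is hypergeometric: P(X = x) = C(L, x) C(50 − L, 25 − x) / C(50, 25). The difference between arms is 2X − L.

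| L | P(arms differ by 5 or more) |
|---|---|
| 10 | 7.4% |
| 15 | 21.7% |
| 20 | 14.8% |

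At L = 15 the standard deviation of the difference is 2 × √(25 × 0.3 × 0.7 × 25/49) = 3.27 patients. With L = 10 or 20 the difference must be even, so five or more means six or more in those rows.

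**2. Shift in the DGF difference with no drug effect.** Shift = (imbalance / 25) × (p_D − p_L).
- The gap p_D − p_L runs from 25 − 8 = 17 points to 45 − 2 = 43 points.
- Five patients: 0.20 × 17 = 3.4 to 0.20 × 43 = 8.6 points. At 5% versus 35% it is 0.20 × 30 = 6.0.
- Six patients: 0.24 × 17 = 4.1 to 0.24 × 43 = 10.3 points.

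**3. Variance removed by stratified allocation plus stratified analysis.** With w = L/50 and p = w·p_L + (1 − w)·p_D, the unstratified variance is 2p(1 − p)/25. The fraction removed is w(1 − w)(p_D − p_L)² / [p(1 − p)].
- Middle (L = 15, 5% v 35%): p = 0.26; 0.21 × 0.09 / 0.1924 = 9.8%.
- Lowest (L = 10, 8% v 25%): p = 0.216; 0.16 × 0.0289 / 0.1693 = 2.7%.
- Highest (L = 20, 2% v 45%): p = 0.278; 0.24 × 0.1849 / 0.2007 = 22.1%.

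**4. Stratified analysis alone, allocation unchanged.** Simulating a Mantel-Haenszel risk difference at 5% versus 35%, the variance falls by about 4-10% as L goes from 10 to 20. At the smallest contrast in the grid the gain is close to nil.

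**5. Type I error and power.** In simulation with L = 15 or 20 and DGF of 5% versus 35% or 45%, the unadjusted chi-square rejects 5.5-5.6% of the time under unstratified 25:25 allocation and 5.0-5.3% under coin-toss allocation. Under stratified allocation it rejects only 3.1-4.2%, so stratifying the list without stratifying the test makes the test conservative. Power to detect a halved risk is 19-28% unstratified and 18-30% with stratified allocation and the same unadjusted test.

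**6. Scale.** The standard deviation of the DGF difference is √(2 × 0.1924 / 25) = 12.4 points in the middle case and about 10-14 points across the grid.

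**The case against.** The strongest reply is that randomisation already deals with this. Chance imbalance is part of sampling error, the test holds its level, and even a five-patient split moves the DGF difference by less than one standard deviation. DGF is one of nine secondary endpoints in a pilot whose primary endpoint is peripheral Treg change, for which no effect is shown here. Power for halved DGF is low regardless: 16% for 20% v 10%, 24% for 30% v 15%, 34% for 40% v 20%. All of this stands, and it limits the point to precision and interpretation.

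A reader might infer that an unrecorded donor type could never be recovered. The documents do not support that. Visit 1 collects transplant data that are not itemised, the list in section 19.3 is not shown to be the whole case report form, and sections 20.5 and 20.6 make the site's medical records the source. Donor type is probably retrievable. What would be lost is the credibility of an adjustment chosen before the data are seen. Cold ischaemia time, donor age and ECD are partial proxies, but no named analysis uses them.

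A reader might also infer that the protocol itself says donor type drives DGF. It does not: it links DGF to ischaemia-reperfusion injury and gives no rates by donor. The contrast used here is an outside assumption.

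Finally, the chi-square sentence sits under the primary outcome heading, and a separate SAP could say more. The finding is about the text supplied.

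**Conclusion.** The point holds as a modest, cheaply removed weakness. Both donor types are eligible, donor type is not among the listed transplant details, and the only named binary test is unadjusted. The DGF comparison is therefore exposed to chance donor imbalance: a five-or-more split has probability 7%, 22% or 15% at 10, 15 or 20 living donors, and a five-patient split moves the difference by 3.4-8.6 points. Stratified allocation plus analysis would remove about 3-22% of the variance; analysis alone removes about 4-10% at 5% versus 35%. All these sizes rest on the assumed donor mix and DGF rates.

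It would be tempting to say that the comparison already carries an imbalance or is biased. The documents do not support that: allocation is random, so there is a risk of imbalance rather than a known one, and the unadjusted test keeps its level near 5%. Nor do they show that stratified randomisation is necessary in a 50-patient pilot.

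**What to change.** 1. Add living/deceased donor to the transplant details in section 19.3 and to the case report form.
2. Pre-specify for DGF a Mantel-Haenszel risk difference stratified by donor type, with a confidence interval, in place of the unadjusted chi-square.
3. Show DGF counts by arm within donor type, descriptively, and state that this is an exception to the exclusion of subgroup analysis in section 19.5.

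**Cost.** One data field and one more pre-specified analysis. Events in the living-donor stratum will be sparse: on the assumptions above, 10 × 0.02 = 0.2 to 20 × 0.08 = 1.6 expected across both arms. The risk-difference scale copes with empty cells, but the variance estimator should be one suited to sparse strata, and that stratum should not be interpreted alone.

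**Optional.** Stratified randomisation is worth considering only if the list is not yet fixed, and only after sections 13.4.1 (simple) and 13.4.2 (blocked, envelopes picked at random) are reconciled. Picking envelopes at random undoes balance within blocks, so stratified blocks would have to be used in sequence. Two lists would also need more than 50 envelopes, because the donor mix is not known in advance, and incomplete blocks could leave arm sizes one or two away from 25/25. If the list is stratified, the analysis must be too.

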13.5 Blinding

This is a double blind placebo study: both the patient and the study team will be blinded to the treatment intervention.

Pharmacy staff who dispense the study medication will not be blinded, nor will Sponsor Office staff responsible for reporting unblinded SUSAR reports to the MHRA.

13.6 Unblinding

The code breaks for the trial will be held in the research office of the renal department and are the responsibility of the CI [name].

If a patient has a significant adverse reaction or a SUSAR then they should stop the study medication and be managed by their clinical team as if the patient was on the active drug. Further advice should be sought from the CI as necessary.

In the event a code is required to be broken a request for unblinding will be made by the Investigator or treating health care professional.

If the person requiring the unblinding is not the CI or their team then the healthcare professional will notify the Investigator team that an unblinding is required for a trial subject which will then occur.

In emergency situations, the responsibility to break the unblinding treatment code resides solely with the CI and will not be delayed in any way. The CI may delegate this duty to the sub-I or senior renal research nurse if there would otherwise be unreasonable delay in unblinding.

On receipt of the treatment allocation details the CI or treating health care professional will continue to deal with the participant's medical emergency as appropriate.

The CI must document the breaking of the code and the reasons for doing so on the CRF/data collection tool, in the site file and medical notes. The CI will ensure it is also documented in the final study report and/or statistical report at the end of the study.

The written information will be disseminated to the Trial Steering Committee.

13.7 Trial Schedule

13.7.1 Schedule of Assessment (in Diagrammatic Format)

Schedule of									Data
visits	Screening	Visit 1	Visit 2	Visit 3	Visit 4	Visit 5	Visit 6	Visit 7	review
Day/Month	Before or	Randomisati	week 1	week 2	week 4	week 8	week 12	2 weeks after	1 yr post
	within 24h	on up to 24h	post	post	post	post	post	stopping	transplan
	post	post	randomisat	randomisat	randomisat	randomisat	randomisat	study	+/- 2
	transplant	transplant	ion (+/- 3	ion (+/- 3	ion (+/- 3	ion (+/- 1	ion (+/- 1	medication	, – weeks
	transplant	transpiant	days)	days)	days)	week)	week)	(+/- 1 week)	WEEKS
Informed								(1) = 110011	
Consent	Х								
Inclusion/									
exclusion									
criteria	Х	x							
Negative									
pregnancy test	х	x	х	х	x	x	x	x	
pregnancy test	^	^	^	^	^	^	^	^	
Demographics	х								
Transplant									
data		х							
Medical									
	Y								Х*
history	x								X*
Randomisation		x							
Study drug									
dispense		x							
Drug									
accountability			х	х	х	х	х		
Dhusiaal									
Physical									
examination		X	X	X	x	x	X	X	
Weight		х	х	х	х	х	х	х	Х*
Vital signs		x	х	х	x	x	x	х	Х*
Concomitant									
medication	X	X	X	X	X	X	X	X	X*
Laboratory									
bloods**		x	x	x	x	x	x	x	Х*
Placed for Two									
Blood for Treg									
quantification		x	x				x	x	
AE assessment		X	X	X	x	x	x	X	Х*
End-point									
assessment							x		

*At this review, the patient's medical records will be reviewed and their clinical data extracted to include:
Graft function as measured by eGFR and serum creatinine
Episodes of rejection
Episodes of infection
Diabetic control measured by HbA1c
Vital signs
Weight
Current medication and anti-diabetic medication regimen

**Laboratory bloods: including fasting c-peptide, cholesterol and serum glucose; serum urea and electrolytes (including creatinine), albumin, alkaline phosphatase (ALP), bilirubin, alanine aminotransferase (ALT), bone profile and C-reactive protein; haemoglobin and HbA1c; and serum save +/- blood for peripheral Tregs as per protocol. The serum save will be taken and processed in keeping with normal protocols but will be used for functional assays to measure the activity of the Tregs at different time points.

13.7.2 Trial assessments

Screening visit

Informed consent Inclusion/exclusion criteria

Documentation of a negative pregnancy test from pre-transplant care

In women of childbearing potential: defined as women following menarche until becoming post-menopausal, unless permanently sterile. Permanent sterilisation methods include hysterectomy, bilateral salpingectomy and bilateral oophorectomy. A postmenopausal state is defined as the absence of menses for 12 months without an alternative medical cause.

Medical history

Demographic data

Concomitant medication

Visit 1 - to occur within 24 hours post-transplant

Inclusion/exclusion criteria

Transplant data

Documentation of a negative pregnancy test

Concomitant medication

Targeted physical examination

Adverse event reporting

Laboratory bloods: including fasting c-peptide, cholesterol and serum glucose; serum urea and electrolytes (including creatinine), albumin, alkaline phosphatase (ALP), bilirubin, alanine aminotransferase (ALT), bone profile and C-reactive protein; haemoglobin and HbA1c; and serum save. Results from bloods that have been taken as part of routine care may also be included on the case record forms.

20ml of blood will also be taken for peripheral Treg quantification.

Vital signs recording

Weight

Randomisation

Study drug dispense

In addition, the renal biopsy specimen collected as per clinical care at time of biopsy will be stained for Treg cell markers.

Visit 2 (1 week post randomisation +/- 3 days))

Check drug adherence Concomitant medication Documentation of a negative pregnancy test Targeted physical examination Weight Vital signs recording

Fasting blood tests: including fasting c-peptide, cholesterol and serum glucose; serum urea and electrolytes (including creatinine), albumin, alkaline phosphatase (ALP), bilirubin, alanine aminotransferase (ALT), bone profile and C-reactive protein; haemoglobin and HbA1c and serum save. Results from bloods that have been taken as part of routine care may also be included on the case record forms. 20ml of blood will also be taken for peripheral Treg quantification.

Adverse event reporting

Visit 3 (2 weeks post randomisation +/- 3 days)

Activities as per visit 2 with exception of blood collection for Treg quantification

Visit 4 (4 weeks post randomisation +/- 3 days)

Activities as per visit 3

Visit 5 (8 weeks post randomisation +/- 1 week)

Activities as per visit 3

Visit 6 (12 week post randomisation +/- 1 week)

Activities as per visit 2 (i.e. additional blood taken for Treg quantification). In addition, patient will stop study medication and then revert back to usual care. Drug accountability (formal) Endpoint assessment

As part of their usual care, and like all patients who undergo a renal transplant, patients have a transplant biopsy at 3 months. This histology specimen will be examined for Treg cell infiltration in addition to standard of care review.

Visit 7 (2 weeks after stopping study medication +/- 1 week)

Patients will have their vital signs and weight recorded, a targeted physical examination, an AE assessment, their laboratory bloods done (as above), blood taken for Treg quantification, and their concomitant medication checked. Female patients will have a pregnancy test.

